**Examples of different forms of contraception:**

Methods	Examples
Highly effective contraception (less than 1% failure rate)	
 
• female sterilization
 
• combination oral contraceptive pill
 
• progestin-only contraceptive pill (mini-pill)
 
• implanted contraceptives
 
• injectable contraceptives
 
• contraceptive patch (only women <198 pounds or 90 kg)
 
• total abstinence
 
• vasectomy (if only sexual partner)
 
• fallopian tube implants (if confirmed by hysterosalpingogram)
 
• combined contraceptive vaginal ring, or
 
• intrauterine devices
 

Effective contraception	
 
• male or female condoms with spermicide
 
• diaphragms with spermicide or cervical sponges
 
• barrier method with use of a spermicide 
 
○ condom with spermicide
 
○ diaphragm with spermicide, or
 
○ female condom with spermicide
 
 
 

Ineffective forms of contraception whether used alone or in any combination	
 
• spermicide alone
 
• periodic abstinence
 
• fertility awareness (calendar method, temperature method, cervical mucus, or symptothermal)
 
• withdrawal
 
• postcoital douche, or
 
• lactational amenorrhea
 

## **10.5. Appendix 5: Liver Safety: Suggested Actions and Follow-up Assessments**

See the Master Protocol CPMP Appendix 6 for liver safety: suggested actions and follow up assessments.

## **10.6. Appendix 9: Provisions for Changes in Study Conduct During Exceptional Circumstances**

### **Implementation of this appendix**

The changes to procedures described in this appendix are temporary measures intended to be used only during specific time periods as directed by the sponsor in partnership with the investigator.

#### **Exceptional circumstances**

Exceptional circumstances are rare events that may cause disruptions to the conduct of the study. Examples include pandemics or natural disasters. These disruptions may limit the ability of the investigators, participants, or both to attend on-site visits or to conduct planned study procedures.

#### **Implementing changes under exceptional circumstances**

In an exceptional circumstance, after receiving the sponsor's written approval, sites may implement changes if permitted by local regulations.

After approval by local Ethical Review Boards, regulatory bodies and any other relevant local authorities, implementation of these exceptional circumstance changes will not typically require additional notification to these groups, unless they have specific requirements in which notification is required (for example, upon implementation and suspension of changes). All approvals and notifications must be retained in the study records.

If the sponsor grants written approval for changes in study conduct, the sponsor will also provide additional written guidance, if needed.

#### **Considerations for making a change**

The prevailing consideration for making a change is ensuring the safety of study participants. Additional important considerations for making a change are compliance with Good Clinical Practice, enabling participants to continue safely in the study and maintaining the integrity of the study.

#### **Informed consent**

Additional consent from the participant will be obtained, if required, for:

- participation in remote visits, as defined in Section “Remote Visits”
- dispensation of additional study intervention during an extended treatment period
- alternate delivery of study intervention and ancillary supplies, and
- provision of their personal or medical information required prior to implementation of these activities.

#### **Changes in study conduct during exceptional circumstances**

Changes in study conduct not described in this appendix, or not consistent with applicable local regulations, are not allowed.

The following changes in study conduct will not be considered protocol deviations.

### Remote visits

**Telemedicine:** Telephone or technology-assisted virtual visits, or both, are acceptable to complete appropriate assessments.

**Mobile healthcare:** Healthcare visits may be performed by a mobile healthcare provider at locations other than the study site when participants cannot travel to the site due to an exceptional circumstance if written approval is provided by the sponsor.

Procedures performed at such visits include, but are not limited to, collection of blood samples, symptom directed physical examinations, ECGs, vital signs, intervention accountability and compliance, AE collection, and collection of health information.

**Other alternative locations:** Laboratory draws may be done at an alternate location in exceptional circumstances.

In source documents and the CRF, the study site should capture the visit method, with a specific explanation for any data missing because of missed in-person site visits.

Regardless of the type of remote visits implemented, the protocol requirements regarding the reporting of AEs, SAEs, and PCs remain unchanged.

Every effort should be made to enable participants to return to on-site visits as soon as reasonably possible, while ensuring the safety of both the participants and the site staff.

### Local laboratory testing option

Local laboratory testing may be conducted in lieu of central laboratory testing. The local laboratory must be qualified in accordance with applicable local regulations.

## CCI

### Study intervention and ancillary supplies (including participant diaries)

When a participant is unable to go to the site to receive study supplies during normal on-site visits, the site should work with the sponsor to determine appropriate actions. These actions may include:

- asking the participant to go to the site and receive study supplies from site staff without completion of a full study visit
- asking the participant's designee to go to the site and receive study supplies on a participant's behalf, and
- arranging delivery of study supplies.

These requirements must be met before action is taken:

- Alternate delivery of study intervention should be performed in a manner that does not compromise treatment blinding and ensures product integrity. The existing protocol requirements for product accountability remain unchanged, including verification of participant's receipt of study supplies.

- When delivering supplies to a location other than the study site (for example, participant's home), the investigator, sponsor, or both should ensure oversight of the shipping process to ensure accountability and product quality (that is, storage conditions maintained and intact packaging upon receipt).
- Instructions may be provided to the participant or designee on the final disposition of any unused or completed study supplies.

### **Adjustments to visit windows**

Whenever possible and safe to do so, as determined by the investigator's discretion, participants should complete the usual Schedule of Activities as described in the Master Protocol CPMP , CPMP(2) DSA, and BP05 ISA. To maximize the possibility that these visits can be conducted as on-site visits, the windows for visits may be adjusted, upon further guidance from the sponsor. This minimizes missing data and preserves the intended conduct of the study.

For participants whose visits have extended windows, additional study intervention may need to be provided to avoid interruption and maintain overall integrity of the study.

### **Documentation**

Sites will identify and document the details of how participants, visit types, and conducted activities were affected by exceptional circumstances. Dispensing/shipment records of study intervention and relevant communications, including delegation, should be filed with site study records.

Source documents generated at a location other than the study site should be part of the investigator's source documentation and should be transferred to the site in a secure and timely manner.

## 10.7. Appendix 10: Abbreviations and Definitions

---

Term	Definition
AE	adverse event
ALT	alanine aminotransferase
AUC	area under the curve
AST	aspartate aminotransferase
CLBP	chronic low back pain
CNS	central nervous system
CPMP	chronic pain master protocol
CRF	case report form; a printed, optical, or electronic document designed to record all of the protocol-required information to be reported to the sponsor for each trial participant.
CCI	
DSA	disease-state appendix
ECG	electrocardiogram
ED	early discontinuation
eGFR	estimated glomerular filtration rate
IB	Investigator's Brochure
ISA	intervention-specific appendix
interim analysis	An interim analysis is an analysis of clinical study data, separated into treatment groups, that is conducted before the final reporting database is created/locked.
MAD	multiple-ascending dose
MoO	Manual of Operations
NOAEL	No observed adverse effect level
NOEL	no observable effect level
NRS	numeric rating scale
participant	Equivalent to CDISC term “subject”: an individual who participates in a clinical trial, either as recipient of an investigational medicinal product or as a control
PC	product complaint
PK	pharmacokinetics

**CCI**

QTc	corrected QT interval
SAD	single-ascending dose
SAE	serious adverse event
SAP	statistical analysis plan
screen	The act of determining if an individual meets minimum requirements to become part of a pool of potential candidates for participation in a clinical study.
SoA	Schedule of Activities
WNOCBP	Women not of childbearing potential
WOCBP	Women of childbearing potential

7.11. Pharmacokinetic/Pharmacodynamic Methods	13
7.12. Safety Analyses	13
7.12.1. Extent of Exposure	13
7.12.2. Adverse Events	14
7.12.3. Deaths, Other Serious Adverse Events, and Other Notable Adverse Events	14
7.12.4. Neurological Exam	14

7.12.5. Clinical Laboratory Evaluation.....	14
7.12.6. Vital Signs and Other Physical Findings	15
7.12.7. Electrocardiograms	15
7.12.8. Suicidal Ideation or Behavior	15
7.13. Subgroup Analyses.....	15
7.14. Protocol Deviations	16
7.15. Interim Analyses and Data Monitoring	16
7.16. Planned Exploratory Analyses	16
7.17. Totality of Evidence for Efficacy	16
7.18. Totality of Evidence for Safety	17
7.19. Annual Report Analyses.....	18
7.20. Clinical Trial Registry Analyses	18
8. Unblinding Plan.....	20
9. References	21

3. Abbreviations and Definitions

Term	Definition
AE	adverse event
ALT	alanine aminotransferase
API	average pain intensity
AST	aspartate aminotransferase
blinding/masking	A single-blind study is one in which the investigator and/or the investigator's staff are aware of the treatment but the participant is not, or vice versa, or when the sponsor is aware of the treatment but the investigator and/or the investigator's staff and the participant are not. A double-blind study is one in which neither the participant nor any of the investigator or sponsor staff who are involved in the treatment or clinical evaluation of the subjects are aware of the treatment received.
BMA	Bayesian model averaging
BP05	H0P-MC-BP05
cLDA	constrained longitudinal data analysis
complaint	A complaint is any written, electronic, or oral communication that alleges deficiencies related to the identity, quality, purity, durability, reliability, safety or effectiveness, or performance of a drug or drug delivery system.
compliance	Adherence to all study-related, good clinical practice (GCP), and applicable regulatory requirements.
CPMP	H0P-MC-CPMP
CTR	Clinical Trial Registry
ECG	electrocardiogram
eCOA	electronic Clinical Outcome Assessment
eGFR	estimated glomerular filtration rate
enroll	The act of assigning a participant to a treatment. Participants who are enrolled in the study are those who have been assigned to a treatment.
FDA	United States Food and Drug Administration
FMQ	FDA Medical Query
GCP	good clinical practice
GFR	glomerular filtration rate

Term	Definition
ISA	intervention-specific appendix
LDA	longitudinal data analysis
LLT	lowest level term
LY	LY3857210
MedDRA	Medical Dictionary for Regulatory Activities
MMRM	mixed-effect model for repeated measures
NRS	numeric rating scale
participant	Equivalent to CDISC term “subject”: an individual who participates in a clinical trial, either as recipient of an investigational medicinal product or as a control
PD	pharmacodynamic
PDEP	preliminary data entry period
PK	pharmacokinetic
CCI	
PT	preferred term
PTEAE	Post-treatment-emergent adverse event
QTcF	Fridericia's corrected QT interval
RMDQ	Roland-Morris Disability Questionnaire
SAP	statistical analysis plan
screen	The act of determining if an individual meets minimum requirements to become part of a pool of potential candidates for participation in a clinical study.
SMQ	standardized MedDRA query
SOC	system organ class
TEAE	treatment-emergent adverse event: An untoward medical occurrence that emerges during a defined treatment period, having been absent pretreatment, or worsens relative to the pretreatment state, and does not necessarily have to have a causal relationship with this treatment.
ToE	totality of evidence
ULN	upper limit of normal
VAS	visual analog scale

4. Revision History

SAP Version 1 was approved on 20 January 2023 prior to unblinding data for Study H0P-MC-BP05 (BP05).

CCI

CCI

- Section 7.12.3: change SMQ to FMQ, which is FDA new standard.

CCI

- Section 7.18: added seizures in the totality of evidence of safety.

5. Study Objectives

5.1. Primary Objective

The primary objective of this ISA is stated in the H0P-MC-CPMP (a) protocol. See Section 7.10.1 for more details on the primary analysis method. For Study BP05, endpoint is defined as 8 weeks post initial treatment administration at Visit 7. Unless otherwise specified, the time point for secondary endpoint measurements is the same as the primary endpoint.

5.2. Secondary Objectives

Secondary objectives applicable to all ISAs are listed in the Study CPMP SAP Version 5.

Additional secondary endpoints specific to Study BP05 are listed in [Table BP05.5.1](#).

Table BP05.5.1. Additional Secondary Endpoints Specific to Study H0P-MC-BP05

Objective	Endpoint Measure
Other Secondary	
Physical Functioning Efficacy of LY3857210 versus placebo	
Mean change from baseline to endpoint in RMDQ total scoreProportion of participants with reduction from baseline of at least 3.5 points in RMDQ total score at each time pointProportion of participants with reduction from baseline greater than or equal to 30%, 50%, and 70% in RMDQ total score at each time pointTime to first treatment response with at least 30%, 50%, and 70% reduction from baseline in RMDQ total score

Abbreviation: RMDQ = Roland-Morris Disability Questionnaire.

5.3. Exploratory Objectives

Exploratory objectives and endpoints specific to Study BP05 are shown in [Table BP05.5.2](#).

6. Study Design

6.1. Summary of Study Design

The CPMP protocol provides a summary of the overall study design for the chronic pain master protocol. ISA-specific study design is provided in the BP05 protocol.

6.2. Determination of Sample Size

Up to approximately 125 participants will be randomized in a CCI to LY3857210 and placebo, respectively. It is expected that approximately 80% of participants, will complete the double-blind treatment period of the study. CCI

CCI

CCI

CCI

If there is no treatment

difference between placebo and LY3857210, the probability of passing the primary objective specified above (that is, false positive rate) is approximately 0.04. The simulation for the power calculation and sample size determination was carried out using the R package simfast v1.3.0.9000.

6.3. Method of Assignment to Treatment

The method of treatment assignment is described in the CPMP SAP Version 5.

7. A Priori Statistical Methods

7.1. General Considerations

The estimand for the primary clinical question of interest has been described in the CPMP SAP Version 5.

Unless otherwise specified, efficacy and safety analyses will be conducted for the 8-week double-blind period and separately for the entire 10-week study period.

Other general considerations for analyses are described in the CPMP SAP Version 5.

7.2. Adjustments for Covariates

The general adjustment strategy has been described in the CPMP SAP Version 5.

Randomization into Study BP05 is stratified by the presence of neuropathic pain as defined by the painDETECT score. Stratification factors included in the models for the primary, secondary, and some exploratory outcomes are shown in [Table BP05.7.1](#).

Table BP05.7.1. Stratification Factor Included in Models for Primary, Secondary, and Exploratory Outcomes

Neuropathic pain	painDETECT score
Positive presence	≥ 19
Unclear or negative	< 19

The painDETECT total score is derived from patient responses to 9 questions on the painDETECT questionnaire. Seven questions ask about the gradation of pain, scored from 0 to 5 (never = 0, hardly noticed = 1, slightly = 2; moderately = 3, strongly = 4, very strongly = 5). One question asks about the pain course pattern, scored from -1 to 2, depending on which pain course pattern diagram is selected. Another question asks about radiating pain, answered as yes or no and scored as 2 or 0, respectively. The final score is between -1 and 38, and a score of 19 or higher suggests that pain is likely to have a neuropathic component (Freynhagen et al. 2006).

7.3. Handling of Dropouts or Missing Data

The missing data strategy has been described in the CPMP SAP Version 5.

7.4. Multiple Comparisons/Multiplicity

There is no plan to formally adjust for multiplicity.

7.5. Use of an “Efficacy Subset” of Participants

There are no plans to use a modified efficacy subset.

7.6. Participant Disposition

The summary of participant disposition has been described in the CPMP SAP Version 5.

7.7. Participant Characteristics

The summary of participant characteristics has been described in the CPMP SAP Version 5.

ISA-specific considerations are described below:

- painDETECT ≥ 19 (that is, positive for neuropathic pain)
- RMDQ total score at baseline.

7.8. Treatment Compliance

Treatment percentage of compliance will be calculated as:

$$\frac{\text{Total pills taken} * 100}{\text{Total pills expected}} \%$$

with total pills taken calculated by total pills dispensed minus total pills returned. A patient is considered to be compliant for a given period if this percentage is between 80% and 120%.

Treatment compliance will be assessed at Visits 5 and 7 (and early discontinuation visit, if applicable); at Visits 4 and 6, the investigational product will not be returned to the site.

Treatment compliance will be reported for the 8 weeks of the treatment period (Visit 3 to 7). The percentage of patients who are compliant with study drug will be summarized by treatment group. For patients who discontinue early, time after the penultimate visit will be excluded for calculation of treatment compliance. For example, if patient discontinued early at Visit 6, treatment compliance will be derived only from data collected through Visit 5. Comparisons between treatment group for treatment compliance will be performed using a Fisher's Exact test. Listings for treatment compliance of individual patients by treatment period will also be provided.

Depending on the level of observed treatment compliance, and where appropriate, sensitivity analyses of primary endpoints may be conducted by excluding patients with poor treatment compliance.

7.9. Concomitant Therapy and eCOA Compliance

The summary and reporting of concomitant therapy and eCOA compliance has been described in the CPMP SAP Version 5. As described in Section 6.2, painDETECT will additionally be included as a covariate for modelling rescue medication.

Concomitant therapy will be reported separately for the 8 weeks of the double-blind period and for the entire 10-week study period.

7.10. Efficacy Analyses

7.10.1. Primary Outcome and Methodology

The analysis of the primary outcome has been described in the CPMP SAP Version 5, and it constrains baseline means to be equal between arms. CCI

CCI

As noted in Section 5, endpoint for the primary analysis is defined as 8 weeks post initial treatment administration.

Calculation of the weekly/bi-weekly time intervals used for analysis of weekly/biweekly mean scores from the eCOA device will follow the algorithm described in the CPMP SAP Version 5, Section 6.12.1, except that the end of the final interval will be determined based on the last VAS collection date, or the last scheduled visit start date if VAS results are missing for the last scheduled visit.

7.10.2. Additional Analyses of the Primary Outcome

Descriptive statistics of primary outcome variables by demographics, disposition, disease characteristics, and treatment administration may be summarized by ISA, in order to examine the population homogeneity assumption between ISAs.

7.10.3. Secondary Efficacy Analyses

Secondary efficacy analyses common to all ISAs within CPMP have been described in the CPMP SAP Version 5. Unless otherwise specified, the time point for secondary endpoint measurements is the same as that for the primary endpoint. Study BP05 will also consider the following secondary analyses.

The RMDQ is a simple, sensitive, and reliable method to measure disability in patients with back pain. The RMDQ consists of 24 statements relating to the person's perceptions of back pain and associated disability based on:

- physical ability/activity
- sleep/rest
- psychosocial
- household management
- eating, and
- pain frequency.

Participants are asked if they feel the statement is descriptive of their own circumstance on that day. The total score is obtained by counting the number of “Yes” responses, ranging from 0 = no disability to 24 = maximal disability.

A Bayesian longitudinal MMRM analysis will be performed to evaluate the change from baseline to each postbaseline visit in the RMDQ total score. The model will utilize the cLDA so that a common mean is estimated at baseline. More details on this approach are provided in the CPMP SAP Version 5.

Information included in the model is shown in [Table BP05.7.2](#).

Table BP05.7.2. Information Included in Bayesian Longitudinal MMRM to Evaluate the Change from Baseline to Each Postbaseline Visit in the RMDQ Total Score

Categorical effects	
 The interaction of treatment and timepoint (constrained to estimate a common mean at baseline across treatments) Average baseline pain severity category (baseline NRS <7, baseline NRS ≥7) Presence of neuropathic pain (painDETECT ≥19, painDETECT <19) Pooled investigative site
Continuous covariates	
 None

Abbreviation: NRS = numeric rating scale.

Other Secondary Analysis

The proportion of participants in each treatment group meeting prespecified binary efficacy outcomes will be calculated for each postbaseline time point and will be used to compare treatment groups. The prespecified binary efficacy outcomes include the proportion of participants:

- with a reduction greater than or equal to 30%, 50%, and 70% from baseline as measured by the RMDQ score, and
- with at least a 3.5-point reduction from baseline in the RMDQ score.

A Bayesian pseudo-likelihood-based categorical repeated measures model will be used to estimate the proportion of participants in each treatment group meeting the prespecified threshold for each postbaseline time interval up to Week 8. These estimates will be used to compare treatment groups. More details on this approach are provided in the CPMP SAP Version 5.

The model will include the categorical and continuous covariates described for the secondary analysis of RMDQ total score.

In addition, time to first treatment response from baseline based on the prespecified binary thresholds above will be assessed. Analyses will be conducted according to the time to event analyses specified in the CPMP SAP Version 5.

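### Table BP05.7.2 crosses only treatment with timepoint in the RMDQ cLDA, so as written it assumes that each covariate's effect is the same at baseline and at Week 8

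*SAP*

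**What the plan says.** SAP section 7.10.3 states: "A Bayesian longitudinal MMRM analysis will be performed to evaluate the change from baseline to each postbaseline visit in the RMDQ total score". On the handling of baseline it adds: "The model will utilize the cLDA so that a common mean is estimated at baseline". The baseline score is therefore modelled as an outcome and not used as a regressor.

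Table BP05.7.2 gives the model content. Its categorical effects are:
- for the randomised comparison, "The interaction of treatment and timepoint (constrained to estimate a common mean at baseline across treatments"
- as the first of three further factors, without any time term, "Average baseline pain severity category (baseline NRS <7, baseline NRS ≥7"
- as the second, again standing alone, "Presence of neuropathic pain (painDETECT ≥19, painDETECT <19"
- as the third and last, the pooled site, also without a time term.

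It lists no continuous covariates. The first entry is written as an interaction and the other three are not.

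Section 7.2 says of the painDETECT factor: "Randomization into Study BP05 is stratified by the presence of neuropathic pain as defined by the painDETECT score". For the rest of the specification, section 7.10.3 says: "More details on this approach are provided in the CPMP SAP Version 5". The general covariate strategy (7.2) and the missing-data strategy (7.3) are deferred to the same document. Table BP05.5.1 places RMDQ change among the other secondary endpoints.

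**The concern.** In an MMRM whose responses are all postbaseline, a covariate entered as a main effect adjusts the postbaseline means directly. In a cLDA the same entry also applies to the baseline response. Without a timepoint term, the model says that participants with NRS of 7 or more differ from the rest by the same RMDQ amount at baseline and at Week 8. It says the same of painDETECT-positive participants and of each pooled site.

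That is doubtful for a category defined by high baseline pain, because such a group can be expected to regress towards the mean. If the assumption fails, the covariates explain less Week 8 variation than they could. If dropout also falls unevenly by arm within a stratum, the misstated mean structure can carry over into the estimated Week 8 difference, even when data are missing at random.

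**Working it through.** The documents give no figure for the RMDQ model, so there is nothing to reproduce.

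**Inputs.** From the documents: about 125 randomised and about 80% completing (Protocol 9.5, SAP 6.2), so 125 × 0.80 = 100 completers; RMDQ range 0 to 24 (SAP 7.10.3). The allocation ratio is redacted. RMDQ SD, visit correlation, stratum shares, covariate effects, RMDQ visit schedule and dropout by arm or stratum are not given, so all are assumed below. The simulations use maximum-likelihood cLDA with unstructured covariance in place of the Bayesian model, whose priors are not shown.

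**Step 1: what the listed terms imply.** For covariate X and treatment T:
- Y0 = m0 + gX + e0
- Y8 = m8 + gX + dT + e8

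The mean change is m8 − m0 + dT, with no X in it. Given baseline, with b the slope of Week 8 on baseline, X enters Week 8 with coefficient g − bg = (1 − b)g.

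If the covariate effect is really g0 at baseline and g1 at Week 8, the coefficient should be g1 − b·g0.

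**Step 2: numbers for a regressing category.** Assume equal SDs and correlation 0.6, so b = 0.6, with g a compromise between g0 and g1.
- g0 = 3, g1 = 1.5: needed 1.5 − 0.6 × 3 = −0.3; imposed 0.4 × (1.5 to 3) = +0.6 to +1.2.
- g0 = 3, g1 = 1: needed 1 − 1.8 = −0.8; imposed 0.4 × (1 to 3) = +0.4 to +1.2.

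The sign is wrong in both cases.

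**Step 3: precision.** Assumed: 125 participants, 1:1, SD 5, baseline to Week 8 correlation 0.6, 30% painDETECT-positive, 40% NRS ≥7, 8 pooled sites, five time points, true difference −1.5, about 20% dropout, 1000 runs. Scenario 1: painDETECT effect 0.5 at baseline and 1.5 at Week 8, NRS effect 3 then 1.5. Scenario 2: 1 then 3, and 3 then 1.
- Scenario 1: SE 0.796 listed, 0.789 crossed; 1 − 0.789/0.796 = 0.9%, worth (0.796/0.789)² − 1 = 1.8% more participants.
- Scenario 2: SE 0.817 listed, 0.795 crossed; 2.7%, worth (0.817/0.795)² − 1 = 5.6% more participants.

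A repeat with separate code gave 0.799 to 0.773 (3.3%).

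**Step 4: bias when dropout differs by arm within stratum.** Same inputs, but about 50% dropout in high-NRS placebo participants and 17% elsewhere. That is 0.4 × 50 + 0.6 × 17 = 30.2% in placebo against 17% on active. True value −1.5; Monte Carlo SE 0.026 in the first two rows.

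| Run | Listed | Crossed | No covariates |
|---|---|---|---|
| Scenario 1 | −1.61 | −1.51 | −1.54 |
| Scenario 2 | −1.64 | −1.51 | −1.58 |
| Separate code, scenario 1 | −1.63 | −1.50 | −1.56 |
| Separate code, scenario 2 | −1.65 | −1.53 | −1.60 |
| 60,000 participants, no site term, scenario 1 | −1.66 | −1.57 | −1.59 |
| 60,000 participants, no site term, scenario 2 | −1.66 | −1.52 | −1.60 |

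The listed form lies 0.09 to 0.14 points from the crossed form, here towards benefit. With constant covariate effects, both forms gave −1.53 in the 60,000-participant run.

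**Step 5: when the bias appears.** Different assumptions: one covariate, 35% in the stratum, SD 5.5, AR(1) correlation 0.7, five visits, true difference 0, large sample, simulation SE about 0.026. In the first four rows dropout is 40% in the active-arm stratum cell and 15% elsewhere. In the last it is 50% in that cell, 5% in the same stratum on control and 15% outside the stratum.

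| Stratum effect, baseline to Week 8 | None | Listed | Crossed |
|---|---|---|---|
| Constant 2 | −0.113 | −0.031 | −0.030 |
| 1 to 3 | −0.145 | −0.068 | +0.014 |
| 0 to 2 | −0.116 | −0.078 | +0.002 |
| 0 to 4 | −0.274 | −0.200 | −0.046 |
| 0 to 4, extreme dropout | −0.451 | −0.316 | −0.024 |

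When dropout differed only by arm (15/25%) or only by stratum (15/35% in both arms), listed and crossed estimates of the difference agreed to within 0.005.

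At n = 125, 1:1, with 40% against 15% dropout, the listed form gave −0.083 (0 to 2) and −0.173 (0 to 4), and the crossed form 0.000 and −0.009, with SEs of about 1.0. Over 1:1 and 2:1 allocation, null rejection at nominal 5% was 4.5-6.3% listed and 4.2-6.5% crossed (600 runs).

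**Step 6: cost of crossing when it is not needed.** With constant effects the SE went from 0.778 to 0.782, which is 0.5% (120 runs).

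**The case against.** The strongest reply is that the table is a list of model content and not an equation, and that the SAP sends the reader to CPMP SAP Version 5 for the approach. Timepoint terms may be specified there. This stands: the documents do not prove that the terms are absent. But the table writes out an interaction where one is meant, so main effects are its natural reading. If the other document differs, the table is incomplete.

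A reader might infer that the covariates adjust nothing. They do drop out of the modelled mean change, but step 1 shows that they enter the Week 8 comparison as (1 − b)g. With a constant effect, the listed form removed as much of the dropout bias as the crossed form did (−0.113 to −0.031).

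A reader might also infer that any uneven dropout biases the result, or that the covariates would be better left out. Step 5 supports neither. Bias beyond that of the crossed model needs both a covariate effect that changes over time and dropout that differs by arm within stratum. The listed form did worse than no covariates only in the regressing scenarios of step 4. Where effects were constant or grew, it did better.

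Finally, the sizes rest on assumed inputs, and the dropout splits are severe. The documents give only overall completion. This stands too, and it limits the priority of the point.

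**Conclusion.** Read as written, Table BP05.7.2 assumes covariate effects that are constant from baseline to Week 8, and so the same mean RMDQ change in every stratum. If that is wrong, the cost under the stated assumptions is about 1-3% of the SE. If dropout also differs by arm within stratum, there is a bias of about 0.1 points against an SE near 0.8 (0.11/0.8 = 0.14 to 0.14/0.8 = 0.18 of an SE in the first two rows of step 4). Its direction depends on which arm and stratum lose participants. No inflation of the rejection rate was detectable.

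This is a cheap, low-priority improvement to one secondary model. A reader might extend it to the primary analysis. The documents do not support that: section 7.10.1 says only that baseline means are constrained equal between arms, and its covariate terms are not visible.

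**What to change.** In Table BP05.7.2, replace the two covariate entries with *baseline NRS category × timepoint* and *painDETECT category × timepoint*. Keep the common-baseline constraint on treatment. Leave pooled site as a main effect: the same algebra applies to it, but crossing it would add many terms for about 125 participants. If CPMP SAP Version 5 already crosses these factors with timepoint, make the table say so.

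Section 7.10.3 carries the same covariates into the RMDQ responder models by reference. Baseline is not a response there, so the argument does not transfer directly; state whether the crossed terms are meant to apply to those models.

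The cost is one line of SAP text and no new data. With five time points (assumed), two two-level factors add 2 × 4 = 8 mean parameters. If the effects are in fact constant, the SE rises by under about 1%.
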